## Potential Problems & Alternative Strategies

**Safety of VLNC cigarette and ECIG products.** The main addictive substance in tobacco is nicotine. Medicinal nicotine products, such as the nicotine patch, gum, and lozenge, as well as a nicotine receptor agonist (varenicline), are all considered the standard of care for smoking cessation [137] and are prescribed to most patients in MD Anderson's Tobacco Treatment Clinic. Providing nicotine replacement is the primary means to alleviating withdrawal and craving, modulating mood, and make it easier for smokers to quit. In terms of non-medicinal nicotine, we have had four MD Anderson IRB-approved protocols where we provided non-medicinal nicotine to study participants, all of which were NIH-funded and monitored by the FDA. In two of our multisite protocols (U54DA031659), 2012-0039 (n=840) and 2014-0510 (n=1250), we provided study participants with NIDA's very low nicotine content (VLNC) research cigarettes for 6 weeks and 5 months, respectively. The purpose of the first study was to evaluate the feasibility and safety of smoking cigarettes with lower nicotine content, while the second study evaluated implementing a gradual vs. immediate reduction in nicotine content. The FDA has suggested that "weaning" smokers off of harmful combustible cigarettes, while promoting less harmful products such as electronic cigarettes, are policies that they are considering [138]. The main outcomes of these first two studies were published in the New England Journal of Medicine [9] and JAMA [139]. The first study demonstrated that smokers would tolerate and use cigarettes containing nicotine as low as 3% of what is found in a typical cigarette, and the second study showed that switching to this VLNC cigarette can be safely done so either gradually or immediately.

Given the concerns around ECIGS, we have conducted an unplanned interim analysis of the adverse events for this protocol. Thus far, we have exposed 176 adult smokers to NIDA's VLNC combustible cigarette for up to 9 weeks and to commercially available closed-tank electronic cigarettes for up to 6 weeks (the same product being used in many other studies across the country). In terms of adverse events, similar proportions of participants have reported adverse events during the exclusive cigarette phases (18.0%) than during the phase where they are encouraged to use electronic cigarettes instead of smoking (15.3%). The most frequently reported adverse events during the electronic cigarette phases included depressive symptoms (n=4), sore throat (n=3), diarrhea (n=2), toothache (n=2), and vomiting (n=2). For the exclusive cigarette phases, the most common adverse events included cough (n=6), irritability (n=5), headache (n=4), back pain (n=2), diarrhea (n=2), limb edema (n=2), insect bite (n=2), nausea (n=2), panic attack (n=2), and urinary tract infection (n=2). No severe adverse event was reported during the electronic cigarette phases, but one was reported during the exclusive cigarette phases, brachycardia (n=1). None of these were determined to be of probable or definitive relation to the device. No serious respiratory symptoms have been reported. Our retention rate through the end of study has been 77%. The preliminary findings suggest that closed-tank electronic cigarettes are not associated with more adverse events than smoking combustible cigarettes.

While this study is designed as a short term experiment, vaping may have long-term side effects that may not be fully known for another decade or two, as was the case initially for combustible cigarette smoking [140]. However, this is all the more reason to study electronic cigarette products, particularly JUUL, the most popular product on the U.S. market. Data from preliminary studies suggest that electronic cigarettes may be relatively safe out to 2 years of exposure among adult cigarette smokers. A study that switched 209 combustible cigarette smokers to electronic cigarettes and followed them for 2 years found that adverse events probably related to electronic cigarettes were experienced by less than 6% of participants, and decreased over time, and none of the 7 SAEs were judged to be related to study product [141]. In terms of short-term exposure, switching to electronic cigarettes results in significant reductions in exposure to numerous toxicants and carcinogens (e.g., NNAL, CEMA, HEMA, 8-

EPI) compared to smoking combustible cigarettes (see [142] for review). Compared to other electronic cigarette products, the JUUL device has several advantages and safety features, including a limit of heating the vapor up to 300 F, and has been found to emit less toxicants. As we mention in the "Safety of the high nicotine dose ECIG" section, independent studies suggest that JUUL ECIGs produce lower levels of free radicals and carbonyls [143], formaldehyde and total aldehyde yields [144], and benzene [145] than other ECIGs, and much lower levels than combustible cigarettes. These initial findings suggest that while certainly not risk-free, electronic cigarettes are likely to be safer than combustible cigarettes over the long term.

**Lack of a cessation endpoint.** If we could, we would be submitting protocols to evaluate electronic cigarettes as a potential smoking cessation aid, because anecdotal evidence suggests that smokers are already doing so. Unfortunately, we are not yet able to evaluate electronic cigarettes as a smoking cessation therapy in the U.S. Smoking cessation is considered a medical indication and products making a medical claim are overseen by CDER, which is a separate and independent component of the FDA from CTP, which oversees tobacco and nicotine regulation. Unlike the pharmaceutical industry, no electronic cigarette manufacturers have taken the necessary steps to assemble a master file needed for obtaining an investigational new drug (IND) application, which must be granted before cessation with electronic cigarettes could be studied. Researchers in the US have been complaining about this conundrum for years but it is not something we can control and in fact we cannot have cessation as an endpoint in any of our studies (except for naturalistic quitting). Moreover, because the focus is on harm reduction, we only select smokers who are not presently interested in quitting for our electronic cigarette studies for ethical reasons.

**Duration of product exposure.** While a one week usual brand smoking is typical for establishing a base rate in most observational studies, the length of the VLNC and each VLNCC+ECIG dose condition (3 weeks each) could be insufficient to determine stable responding. However, in our preliminary studies we observed little change in CPD for VLNCCs beyond week 3. There is no data to estimate length of exposure to e-cigs needed to establish stable responding, but we feel 3 weeks is sufficient since individuals in the high dose condition will receive levels of plasma nicotine comparable to combustible cigarettes within as little as 10 puffs, and this will provide the intended contrast to the lower plasma nicotine levels of the low dose e-cig within the same time frame.

Another potential issue is that the length of the phases may be insufficient to sample ITS smoking behavior. However, Shiffman and colleagues, who have done the most sophisticated work with this population, have used a 21-day (3 week) sample in EMA studies [73]. Additionally, it may be difficult to estimate the "typical" TNE and MA among ITS given their low frequency of smoking. To address this, we collect urine samples twice per week (in Phases 2, 3, and 4) to better estimate these compounds among ITS, and like Shiffman and colleagues [8], we will select for analysis the sample that most closely corresponds in time to smoking their median CPD from Phase 1. If the participant fails to bring in any/all samples, a deviation will not be logged. A spot urine collection will be conducted during the visit in the event no samples are returned.

Finally, rather than conduct random EMA assessments for the entire duration of the study, which would quite burdensome to participants, we have elected to conduct daily diary assessments (once per day) in phases 2-4 and to implement random (up to 2 times per day) assessments only in phases 3 & 4. We feel this is a reasonable trade off to reduce participant burden since our primary interest in the EMA data pertains to the assessment of frequency and circumstances surrounding dual product use. In addition, EMA information during regular smoking has been thoroughly explored for DS and ITS by Shiffman and colleagues [70, 71, 73, 75, 76].

**Nonrandom ECIG flavor assignment.** By allowing participants to choose a preferred flavor, we will be unable to determine the influence of this factor on our dependent measures in a prospective manner. At most, we will be able to determine the influence of ECIG flavor on our outcome measures in an exploratory fashion (e.g., post hoc sub-group analyses). However, we chose this design to maximize the likelihood that participants will actually use the study ECIG devices during the product exposure period. Recent studies suggest that most ECIG users (over 65%) prefer some type of flavoring, usually a sweet flavor [146]. Moreover, many menthol users specifically eschew any use of nonmenthol products, and thus may find nonmenthol ECIG flavors unpleasant. Thus, in order to sustain ECIG use, we believe it is more important to propose a design that accommodates participant product preference, rather than expose them to a flavor they wouldn't use. We are aware that the FDA is considering a complete or partial flavoring ECIG ban [147]. If such a ban were to occur at a federal (or state) level, we would comply by only offering participants flavor choices allowed by law, which is likely to be tobacco- and possibly menthol-flavored [148] products.

**Safety of the high nicotine dose ECIG.** JUUL ECIGs currently comprise over 75% of the U.S. market [2] and have some of the highest nicotine concentrations among ECIG products. Safety studies regarding JUUL ECIGs are relatively few, owing to the newness of the product, but these initial studies suggest that the 5% solution (~59 mg/ml of nicotine) produce blood nicotine values and pharmacokinetic profiles comparable to those of combustible cigarettes, but with less toxicants. For example, studies sponsored by JUUL Labs, Inc., have found that JUUL ECIGs produce nicotine pharmacokinetic profiles in adults similar to that of combustible cigarettes [149], with lower levels of toxicants, including volatile organic compounds, polycyclic aromatic hydrocarbon, carbonyls, and ammonia compared to combustibles [150]. In terms of independent verification of JUUL ECIG's nicotine content, one study of adolescent and young adults found that JUUL ECIGs product cotinine levels, the major metabolite of nicotine, similar to those of combustible cigarettes [151]. Another recent study by independent researchers found that JUUL ECIGs produced saliva cotinine levels that the authors noted were comparable to their previous evaluations of lower-dose ECIGs and combustible cigarettes among adults [152]. In terms of toxicants, independent studies suggest that JUUL ECIGs produce lower levels of free radicals and carbonyls [143], formaldehyde and total aldehyde yields [144], and benzene [145] than other ECIGs, and much lower levels than combustible cigarettes. Thus, preliminary data from both independent and industry-sponsored labs suggest that the high-dose JUUL ECIG product produces comparable blood levels of nicotine, and lower levels of toxicants, than combustible cigarettes among adults.

Using a high nicotine dose ECIG such as JUUL may increase nicotine dependence. However, it should be noted that smokers titrate their nicotine level all through the day to maintain the level they are accustomed to, given nicotine's short half-life [153]. In studies of the topography of smoking where smokers are provided with nicotine patches, they automatically smoke less of each cigarette and inhale less deeply [154]. A similar nicotine self-titration appears to occur among electronic cigarette users in studies conducted over 12 [155] and 24 months [156] of product exposure. While it is possible that some smokers who use the JUUL device may experience an increase in nicotine levels and possibly dependence, which we mention in the "Adverse experiences associated with electronic cigarettes" paragraph of the Protection of Human Subjects section, there is no evidence to date to show that dual product users are any more nicotine dependent than exclusive users of combustible cigarettes. We also describe that we will offer all participants 8 weeks of free smoking cessation treatment, including nicotine replacement therapy and smoking cessation counseling, at the end of their study participation, if they wish to do so. This treatment will be provided by MD Anderson's Tobacco Treatment Program under the guidance of [name], the medical director of that program and medical monitor of this protocol.

**Future directions.** At the project's conclusion we will have identified the extent to which DS and ITS compensate for a loss in available nicotine while using VLNCCs, by using e-cigs that provide varying levels of plasma nicotine delivery. We will also identify factors that influence dual use of VLNCC and e-cigs, toxicant exposure as well as product liking and reinforcement. We will use this data to pursue future studies examining the potential for e-cigs to serve as a cessation aid for those interested in quitting as well as a vehicle for harm reduction among those that do not.

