**Financial Compensation for VLNCC compliance.** We know from our U54 that some participants smoked UB cigarettes during the VLNCC condition (~2-3 CPD). However, the effect of non-compliance was negligible, as TNE, our primary measure of nicotine compensation, dropped significantly by week 3 relative to UB smoking (See **Figure 1**). Such would be the case here as well, although in this study we will provide incentives for VLNCC compliance. In our recent unpublished inpatient study, 23 smokers smoked only VLNCC 0.03 mg cigarettes for one week, while 7 others were permitted to "cheat" by allowing them to smoke 1-2 UB cigarettes in addition to the VLNCC's. We determined that a 0.02 nmol/ml cut-off for anatabine (a minor tobacco alkaloid) would identify non-compliance with smoking the 0.03 VLNCC exclusively, by as few as 1-2 UB cigarettes. Anatabine is derived from tobacco and is not affected by e-cig use, whereas TNE is influenced by nicotine from either combustible or non-combustible sources. Thus, anatabine provides an excellent measure of VLNCC compliance. Subjects will be told that compliers (<0.02 nmol anatabine) will receive a \$100 bonus in phases 2 (VLNCC) and 3 & 4 (VLNCC+ECIG). Honest reporters of UB above this level will receive a \$10 bonus, while those above this level who do not report UB use will receive no bonus.

COVID-19 adaptation: No adaptations needed.

**Sample collection and biomarker analyses.** A urine sample (TNE and MA) will be obtained at each visit starting at Visit 1. In addition, participants will be asked to collect a urine sample at home twice a week between appointments, which will be collected at their subsequent appointment. This will allow for better assessment of TNE and MA exposure among low frequency smokers. Smartphones will be used to prompt the participant to obtain the sample. If the participant fails to bring in any/all samples, a deviation will not be logged. A spot urine collection will be conducted during the visit in the event no samples are returned. Urine samples will be sent to the University of Minnesota for analysis. Samples will be de-identified containing only the subject ID generated by the study database, visit number, code corresponding to type of sample, vial number and date collected (example, 456123-03-2-5 9/1/2018).

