COVID-19 adaptation: Participants also will be asked to collect a urine sample at home on or near the day of their virtual "in-person" visits, starting at Visit 1. For ease of remote collection, we will only ask for participants to complete one urine collection on or near the time of their visit. We will provide postage-paid supplies for participants to ship these samples to the study team for proper storage and analysis.

Total Nicotine Equivalents (TNE) is the sum of total nicotine, total cotinine, total 3'-hydroxycotinine and nicotine N-oxide excreted in urine ("total" refers to the analyte and its glucuronide conjugate) comprise 85 to-95% of the nicotine dose received by a tobacco user [118], and is an excellent biomarker of nicotine uptake, directly measuring a high percentage of the nicotine dose. TNE will be analyzed by liquid chromatography-electrospray ionization-

tandem mass spectrometry (LC-ESI-MS/MS) [119, 120]. Use of TNE will enable us to quantify changes in nicotine exposure through each phase of the study and will be *our primary measure of nicotine compensation between baseline and subsequent conditions*.

Minor Tobacco Alkaloids (MA) will be analyzed using the LC-ESI-MS/MS method [121, 122]. While nicotine is accepted as the major addictive compound in tobacco, several other constituents, such as MA (e.g., anabasine, anatabine, and nornicotine), may also play a role, and the potential differences in these compounds as a function of ECIG and VLNCC use is of interest. *MA will allow us to estimate differential use in combustible vs. e-cig use, and anatabine will allow us to determine smoking of VLNCC vs. UB.*

Quality Control Procedures. Multiple urinary aliquots will be prepared, labelled, and frozen. With each set of samples, 2 aliquots are analyzed. If the results from these 2 aliquots do not agree within 10% of the known amount, then that set of samples is reanalyzed. Negative controls are also included with each set analyzed.

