### **Statistical Approach & Expected Outcomes**

**General Data Analytic Approach.** We will conduct repeated measures analyses (i.e., across time) using generalized linear mixed modeling (GLMM; Proc MIXED, Proc GLIMMIX, and Proc MCMC; SAS 9.4). Continuous and count data will be analyzed using linear and Poisson regression, respectively (Proc GENMOD; SAS v. 9.4). Evaluation of distributional assumptions will use residual plots and, where possible, formal statistical tests. Depending upon statistical technique, we will address violations of assumptions using transformations, robust estimators, stratification, and/or scaling coefficients. For instance, given the characteristically skewed nature of the TNE distribution the analytic plan and power discuss this variable in its log form. Analyses of data with missing values will utilize multiple imputation for cross-sectional analyses (Proc MI and Proc MIANALYZE; SAS v.9.4) [126], while analyses of repeated measures will rely on GLMM to maximize use of existing data. For analyses that require assessment for differential patterns of missing data, we will use Little's Test of MCAR for continuous outcomes and the Park and Lee's approach for discrete outcomes [127, 128]. We will use pattern-mixture modeling methods to address non-ignorable missing data patterns [129]. We will use sensitivity analyses to evaluate the robustness of findings to missing data assumptions. Finally, the False Discovery Rate approach will be used to correct for multiple testing [130].

***Aim 1: To characterize the effects of switching to VLNCCs plus ECIG-Hi or ECIG-Lo nicotine doses on abuse liability among daily and intermittent smokers.*** Our primary measures of abuse liability will be CPD (product use) and nicotine equivalent (TNE) levels (nicotine compensation). We hypothesize that compared with the VLNC+ECIG-Lo phase, smokers will show decreased CPD and TNE levels during the VLNC+ECIG-Hi phase. To address these hypotheses, we will use GLMM to evaluate the effects of ECIG dose on measures of nicotine abuse liability, including cigarettes per day and TNE levels.

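### For intermittent smokers, the urine sample analysed for TNE in Phases 2-4 is chosen by CPD reported after assignment, and the rule conflicts with the end-of-phase timing stated elsewhere and cannot be applied uniformly

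*Combined protocol and SAP*

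**What the plan says.** The rule is in Potential Problems & Alternative Strategies, under Duration of product exposure. The stated difficulty is that of estimating typical "TNE and MA among ITS given their low frequency of smoking". The remedy is home urine twice a week in Phases 2, 3 and 4, after which "we will select for analysis the sample that most closely corresponds in time to smoking their median CPD from Phase 1". If nothing is brought back, "A spot urine collection will be conducted during the visit in the event no samples are returned".

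Other sections bear on this:

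- Study overview (Assessment of nicotine abuse liability) says that, for Aims 1 and 2, TNE and minor alkaloids (MA) are assessed when each phase ends. It mentions no selection.
- Measures takes urine at every session after screening, starting at Visit 1. The COVID-19 adaptation asks for a single sample on or near the visit day.
- Statistical Approach, Aim 1, makes CPD and TNE the primary measures and predicts that "smokers will show decreased CPD and TNE levels during the VLNC+ECIG-Hi phase". It does not refer to the selection rule.
- Measures calls TNE "our primary measure of nicotine compensation between baseline and subsequent conditions" and notes that "TNE is influenced by nicotine from either combustible or non-combustible sources".
- Baseline Screening places randomisation at Visit 1, after Phase 1. The daily diary starts in Phase 2.

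**The concern.** The target of the rule is a baseline quantity, but locating the day that matches it is not. It needs each participant's CPD during Phases 2-4, which is itself a primary outcome. TNE is therefore read on days picked by the other outcome. If smoking falls as Table 1 expects, the analysed day is one on which the participant smoked roughly as on usual brand, not a typical day of that phase.

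Consistency is also at stake. The rule needs several samples to choose from. Where there is only one, the analysed TNE is unselected. ITS TNE would then mix two definitions, divided along phase and visit mode. A change from Phase 1 to a later phase could partly reflect the change in definition.

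**Working it through.** **1. The plan's own figure.** Inputs are the ITS log(TNE) rows of Table 1, the posited correlation of 0.4 and n = 67.

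- SD of the paired difference = sqrt(0.80² + 1.29² - 2 × 0.4 × 0.80 × 1.29) = sqrt(1.4785) = 1.216.
- dz = (3.07 - 2.31)/1.216 = 0.76/1.216 = 0.625, against 0.63 in Table 2.
- Two-sided paired t-test, alpha 0.05, n = 67: power 99.9%, against at least 99% in Table 2.

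The calculation reproduces; it takes no account of the rule. Table 1 has TNE higher on ECIG-Hi, while Aim 1 predicts it lower. That is a separate matter, and only the absolute size 0.76 is used here.

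**2. Where the rule can operate.**

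| Setting | Samples to choose from | Selection possible? |
|---|---|---|
| Phase 1 | visit sample only | no |
| Phases 2-4, in person, home samples returned | about 2 × 3 = 6 | yes |
| Phases 2-4, in person, none returned | one spot sample | no |
| Virtual visit | one | no |

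**3. Illustrative shift of a phase mean.** The documents give no day-level data, so these inputs are assumed: gamma-Poisson daily CPD (shape k = 0.5, 1 or 2), 21 days, six fixed sample days, within-person SD of log(TNE) 0.4-0.8, and day-level correlation between CPD and log(TNE) of 0 or 0.3-0.5. Targets are medians of seven simulated Phase 1 days at Table 1's 3.42 CPD.

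Shift = (mean CPD on selected day - phase mean)/sqrt(m + m²/k) × (correlation × SD), where m is the phase mean CPD. Correlation × SD is 0, or runs from 0.3 × 0.4 = 0.12 to 0.5 × 0.8 = 0.40.

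At 1.57 CPD, taking the largest product:

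- All-days median, k = 0.5: (1.38 - 1.57)/2.55 × 0.40 = -0.03.
- All-days median, k = 2: (2.05 - 1.57)/1.67 × 0.40 = +0.12.
- Smoking-days median, k = 2: (2.30 - 1.57)/1.67 × 0.40 = +0.17.

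With zero correlation every shift is 0; with a negative one the signs reverse. For scale, the planned ITS difference between Phase 1 and ECIG-Hi is 3.31 - 3.07 = 0.24, and between Phase 1 and ECIG-Lo 3.31 - 2.31 = 1.00.

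**4. The randomised Hi-v-Lo contrast.**

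- Equal CPD on both doses (1.57 each in Table 1) and the same day-level relation: about 0.
- CPD ratio 1.40, the minimum detectable ITS ratio in Table 2 (1.83 v 1.31), same relation: up to about 0.10 over fixed targets of 0 to 3. If it all counts as a loss: 0.76 - 0.10 = 0.66, dz = 0.66/1.216 = 0.54, power 99.2%.
- Relation on one dose only, using the +0.17 shift as a loss: 0.76 - 0.17 = 0.59, dz = 0.49, power 97%.
- Opposite slopes per cigarette (assumed -0.2 on Hi, +0.1 on Lo), selected day one cigarette above the phase mean: 0.76 + 1.0 × (-0.2 - 0.1) = 0.46, dz = 0.38, power 86%.

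**5. The undefined median.** ITS smoke on 4 to 27 days a month. With independent days and a 30-day month, the all-days median of seven Phase 1 days is 0 with probability P(Bin(7, d/30) ≤ 3): 99% at d = 4, 91% at 8, 50% at 15, 9% at 22. A smoking-days median does not exist if Phase 1 has no smoking day: (1 - d/30)^7 = 37% at d = 4 and 11% at d = 8.

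**The case against.** The rule is stated in advance, follows a cited biomarker study in daily and non-daily smokers, uses the same baseline target on both doses and never looks at TNE. A reader might infer that values are picked after the fact; the text does not support that. Matching could also serve a legitimate question, intake at comparable smoking. That stands, but it is not the typical exposure the section sets out to estimate.

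Timeline follow-back is done at Visit 1, so it is the evident source of Phase 1 CPD although the rule does not name it. The cited study may define the median and the handling of ties; the protocol does not.

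A reader might also infer that the primary Hi-v-Lo result for TNE is seriously biased. The documents do not support this. Table 1 plans equal ITS CPD on both doses, and the adverse same-relation case costs 0.10 of 0.76. What keeps the question open is that Aim 1 predicts lower CPD on Hi, and e-cigarette nicotine enters TNE, so the CPD-TNE link could differ by dose.

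Finally, fixing the target at 0 for everyone at 1.57 CPD gives a phase shift as large as -0.32. That pairing is not credible: at Table 1's 3.42 CPD a zero all-days median arises in only 21%, 5% and 1% of simulated participants (k = 0.5, 1, 2). Participants for whom it is likely smoke on far fewer days.

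**Conclusion.** The concern holds as a defect of definition and consistency in the ITS TNE and MA values. One primary measure selects the other after assignment, two sections disagree on which sample counts, and the rule cannot run in every phase or visit mode. None of this depends on the simulation.

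The numerical consequence is uncertain. Size and direction cannot be derived from the documents, and zero is possible. Under the stated assumptions the phase shift is modest in absolute terms, but up to half (0.12/0.24) or about 70% (0.17/0.24) of the planned Phase 1 v ECIG-Hi difference. ITS comparisons with Phase 1 and across phases, exploratory under Aim 3, are therefore the most exposed. The Hi-v-Lo contrast is about unbiased if CPD and its link to TNE are alike on both doses. Otherwise the bias is probably small, and larger only if that link differs by dose. Table 1's ITS inputs come from a low-CPD subset of an earlier trial (below 7.3 CPD), so they are weak. Daily smokers are not affected.

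**What to change.** Reconcile the Study overview with the Duration of product exposure paragraph, and carry the result into the Aim 1 analysis text:

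- Make the end-of-phase visit sample the primary ITS value for TNE and MA in every phase and visit mode. Say that it is taken whether or not home samples are returned.
- Where home samples are assayed, enter all of them as repeated log(TNE) values in the GLMM for Hi v Lo, without selection on CPD.
- Keep the CPD-matched sample as a sensitivity analysis. Define the median (all days or smoking days, from timeline follow-back), a tie rule, and a fallback if the target is never reached or does not exist.

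The cost is a few sentences and no new collection. For 80 ITS before attrition, visit samples need 80 × 4 = 320 assays over Phases 1-4; assaying all home samples adds up to 80 × 3 × 6 = 1,440. The documents do not say which samples would be assayed anyway. The real price is noise: one visit sample represents a low-frequency smoker less well. With the assumed within-person SD of 0.4-0.8, the mean of six independent samples would have an SD of 0.16-0.33 (SD/√6). The present rule also analyses a single sample per phase, so it does not gain that precision either.
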